**Exploratory Objectives**

- To conduct pharmacogenomic evaluations of OS, PFS and other endpoints in subjects with and without mutations in BRCA1 or BRCA2.
- To evaluate patient-reported outcomes (PROs).

**2.2. Hypothesis**

Trabectedin in combination with DOXIL will improve OS compared with DOXIL monotherapy in the treatment of subjects with platinum-sensitive advanced-relapsed epithelial ovarian, primary peritoneal, or fallopian tube cancer who received 2 previous lines of platinum-based chemotherapy.

**3. STUDY DESIGN AND RATIONALE****3.1. Overview of Study Design**

This is a randomized, open-label, active-controlled, multicenter study designed to assess the efficacy and safety of trabectedin+DOXIL as a third-line chemotherapy in subjects with platinum-sensitive advanced-relapsed epithelial ovarian, primary peritoneal, or fallopian tube cancer who received 2 previous lines of platinum-based chemotherapy. Approximately 670 adult subjects will be enrolled in this study, with 335 subjects per planned treatment group. At randomization, subjects will be stratified by 4 criteria: 1) the time from the last dose of first-line platinum therapy to disease progression (6 months to 12 months vs >12 months to 24 months vs >24 months), 2) Eastern Cooperative Oncology Group (ECOG) performance status grade (0 vs 1), 3) BRCA 1/2 status (mutation vs no mutation), and 4) prior DOXIL therapy (no vs yes). Subjects will then be randomly assigned in a 1:1 ratio to the trabectedin+DOXIL combination therapy group (Arm A) or to the DOXIL monotherapy group (Arm B).

During the treatment phase, subjects will receive study drug by IV infusion on Day 1 of a 21-day cycle in Arm A and on Day 1 of a 28-day cycle in Arm B. Treatment will continue until the occurrence of disease progression or unacceptable treatment toxicity, or until 2 cycles after assessment of a complete response (CR). Subjects assigned to the trabectedin+DOXIL group (Arm A) will be pretreated with 20 mg of dexamethasone IV, or an equivalent IV corticosteroid, approximately 30 minutes prior to initiation of infusion of DOXIL on Day 1 of each treatment cycle.

Subjects will be followed for survival at least every 8 weeks for the first 2 years after the treatment termination visit and approximately every 12 weeks thereafter. This study will end 2 months after the last subject has received the last dose of study drug, when 514 deaths have been observed, or until the clinical cutoff date.

The analysis of the primary endpoint, OS, will be conducted after at least 514 events (deaths) are observed or up to the clinical cutoff date. An interim analysis is planned for this study (after observing 60% [308 death events] of the total number of required [514] death events) to determine whether efficacy has been adequately demonstrated, allowing for early study termination and subject crossover from the monotherapy arm. Given the findings from Study ET743-OVA-301, which demonstrated superior PFS and a favorable survival trend for the trabectedin+DOXIL combination therapy, there are no plans to conduct a futility analysis at the interim analysis.

Secondary efficacy endpoints of PFS and ORR will be assessed using the Response Evaluation Criteria in Solid Tumors (RECIST, Version 1.1). Scheduled assessments of disease status will be performed within 30 days before randomization, every 8 weeks ( $\pm 5$  days) after randomization for the first 4 assessments, and then every 12 weeks ( $\pm 5$  days) thereafter. Disease assessments, including assessments for subjects who discontinue treatment for reasons other than disease progression, will be performed until disease progression is radiographically confirmed, the start of subsequent anticancer therapy, withdrawal of subject consent, or the clinical cutoff date. For subjects who discontinue study treatment, documentation of all subsequent anticancer therapy, survival status, and safety evaluations as outlined in the Time and Events Schedule will be required. Survival status should be recorded at least every 8 weeks for the first 2 years after the treatment termination visit and approximately every 12 weeks thereafter. Collection of survival status will continue until at least 514 deaths have been observed or until the clinical cutoff date.

The primary efficacy endpoint is OS, defined as the time between randomization and death from any cause. Secondary endpoints are PFS (defined as the time between the date of randomization and the date of disease progression or death), and ORR (defined as the proportion of subjects who achieve CR or partial response [PR]).

Safety will be assessed using laboratory test results and the incidence and severity of adverse events. Left ventricular ejection fraction assessments (either multigated acquisition [MUGA] scans or 2-dimensional echocardiograms [2D-ECHO]) and electrocardiograms (ECGs) will be used to monitor cardiac function.

An IDMC will assess safety and efficacy data (Section 11.9, Independent Data Monitoring Committee). Safety data will be reviewed approximately every 6 months. A final cardiac analysis will be conducted and a report will be provided. An interim analysis of OS will be performed after approximately 308 subjects have died. The final analysis of OS will occur when at least 514 deaths have been observed or until the clinical cutoff date.

A Study Steering Committee will periodically review issues related to study conduct and offer advice as needed. The Steering Committee is composed of physicians who have extensive

experience with both trabectedin and the treatment of ovarian cancer. The Steering Committee will meet with the Study Team periodically to review the study status and make recommendations for actions to take with regard to study recruitment, data gathering, and data review. The Steering Committee will not have access to unblinded data listings or summary analyses during the study.

[figure not shown]
Supportive care (eg, antibiotics, analgesics, transfusions) may be provided according to institutional standards. Appropriate prophylactic antiemetic regimens may be provided, as necessary. No concurrent investigational agents or antineoplastic agents will be permitted.

It is anticipated that the volumes of blood drawn for each subject for routine laboratory evaluations throughout the study will be approximately 15 mL for screening serum chemistry and hematology tests; 10 mL for BRCA 1/2 testing at screening (for subjects who do not have a known BRCA 1/2 status); 4 mL for subjects consenting to the optional pharmacogenomics component of the study (where local regulations permit); 45 mL and 60 mL for treatment Arms A and B, respectively, per cycle for serum biochemistry and hematology tests; 4 mL per scheduled CA-125 sample; and 24 mL from those subjects who provide PK samples.

All subjects who discontinue study treatment will be monitored for survival. The subject will have completed the study when the study is terminated or the subject has died or has withdrawn consent for follow-up.

A diagram of the study design is provided below ([Figure 4](#)).

Figure 4: Study Design

Note: On 26 June 2017, the IDMC requested a futility analysis of OS to be performed at the time of the next meeting 6 months later. In view of the IDMC request, study data up to 20 September 2017 were evaluated for safety and OS (45% rather than 60% of the required death events at the planned interim analysis). Following the review of the study data by the IDMC on 15 December 2017, the HR for OS was 0.962, crossing the previously agreed upon threshold for futility of 0.93. In view of this result and the observed and expected higher toxicity in Arm A as compared with Arm B, the IDMC recommended discontinuing the study. Therefore, as of Amendment 6, no new subjects will be randomized to study treatment, and treatment with trabectedin should be immediately discontinued for subjects assigned to Arm A (trabectedin+DOXIL). All study subjects (Arm A or Arm B) currently on study who, in the opinion of the investigator, are deriving clinical benefit may continue treatment with single-agent DOXIL as per the local standard of care. Treatment for these subjects may continue as long as the subjects comply with protocol-specified prohibitions and restrictions for treatment

(Section 4.3) and as long as they experience clinical benefit in the opinion of the investigator. DOXIL will be provided by JR&D as needed until post-trial access to DOXIL is available or until disease progression, whichever occurs first.

Accordingly, the end of study data collection is defined as when all subjects on study treatment have completed treatment termination visit assessments as specified in the Time and Events Schedule for Amendment 6 or by 18 January 2018, whichever occurs first. For subjects continuing treatment with single-agent DOXIL, as per the local standard of care, only serious adverse events should be reported to JR&D as outlined in Section 12.3.2.

### 3.2. Study Design Rationale

Most ovarian cancer patients are diagnosed with advanced disease, resulting in poor prognosis with inferior survival. Despite high rates of objective responses to the combination of cytoreductive surgery and platinum-based chemotherapy, disease often relapses. The results of second-line treatment depend largely on the PFI after the last dose of first-line therapy, with patients exhibiting a longer PFI having a better response to subsequent chemotherapy. Unfortunately, the response is of relatively short duration, and most patients require a third line of chemotherapy. There are very few published studies of chemotherapy administered after 2 lines of platinum-containing regimens to inform the choice of chemotherapy in the third-line setting, even though relapse of epithelial ovarian cancer is common. Study ET743-OVC-3006 is designed to investigate the activity of trabectedin+DOXIL for the treatment of subjects with platinum-sensitive advanced-relapsed epithelial ovarian, primary peritoneal, or fallopian tube cancer who have received 2 previous lines of platinum-based chemotherapy.

#### Randomization

Randomization will be used to minimize bias in the assignment of subjects to treatment groups, to increase the likelihood that known and unknown subject attributes (eg, demographic and baseline characteristics) are evenly balanced across treatment groups, and to enhance the validity of statistical comparisons across treatment groups.

Following Amendment 6, subjects will not be randomized to study treatment, and no new subjects will be screened. Subjects currently in screening are eligible to receive treatment with single-agent DOXIL, if the investigator confirms that such treatment would be a clinically appropriate therapeutic option.

#### Pharmacokinetic Sample Collection

A population PK model has been developed using data from 15 studies performed in patients with solid malignancies, including 3 studies (ET-743-INT-11, ET-B-009-9, and ET-OVA-301) in subjects with ovarian cancer. Blood samples for population PK analysis will be collected using a sparse sampling scheme from at least 40 subjects in the trabectedin+DOXIL combination treatment group. These data will be analyzed using a population PK model to characterize the PK of trabectedin in the patient population enrolled in the present study.

## BRCA 1 and BRCA 2 Mutations

The mechanisms of action of both trabectedin and DOXIL involve DNA damage. BRCA 1/2 is part of the homologous recombination repair (HRR) machinery responsible for DNA repair. This study will attempt to build on existing data by investigating the association of BRCA 1/2 mutation status with OS, PFS, and other endpoints by stratification based on BRCA 1/2 mutation status (mutation vs no mutation) prior to randomization.

### 4. SUBJECT POPULATION

Following Amendment 6, in those instances where the investigator confirms that single-agent treatment with DOXIL would be a clinically appropriate therapeutic option for subjects in screening, those subjects in screening would need to meet study inclusion and exclusion criteria as specified in Sections 4.1 and 4.2.

The inclusion and exclusion criteria are described in the following 2 subsections. If there is a question about the inclusion or exclusion criteria below, the investigator should consult with the appropriate sponsor representative and resolve any issues before enrolling a subject in the study. Waivers are not allowed.

Prior to randomization, inclusion criteria #4 through #8 must be reviewed by sponsor's medical monitor. Note: As of Amendment 6, subjects will not be randomized to study treatment.

#### 4.1. Inclusion Criteria

Each potential subject must satisfy all of the following criteria to be enrolled in the study. Each subject must:

1. Be a woman 18 years of age or older.
2. Have histologically proven advanced-relapsed epithelial ovarian, primary peritoneal, or fallopian tube cancer.
3. Have an ECOG performance status grade of 0 or 1.
4. Have received first-line treatment with a platinum-based regimen and had no evidence of disease progression for  $\geq 6$  months after the last dose.
5. Criterion modified per amendment
  - 5.1 Have received second-line treatment with a platinum-based regimen, with progression of disease after attaining a response. A response could have been determined by imaging or by serum CA-125 levels.
6. Criterion modified per amendment
  - 6.1. Have progression of disease based on imaging after the second-line platinum-based regimen.
    - Subjects treated with a DOXIL-containing regimen as a second-line therapy are eligible if subsequent disease progression occurs  $\geq 9$  months from the first dose.

- 
7. Criterion modified per amendment
    - 7.1 Per Amendment 6, subjects no longer need to have disease response and disease progression events as noted in criteria #5 and #6 reviewed by the sponsor's medical monitor prior to randomization.
  8. Have evidence of measurable disease at screening as evaluated by RECIST (Version 1.1) criteria ([Attachment 2](#)).
  9. Criterion modified per amendment
    - 9.1 Per Amendment 6, subjects no longer need to be able to receive IV dexamethasone or an equivalent IV corticosteroid.
  10. Have a known BRCA 1/2 mutation status. For subjects who do not have a known BRCA 1/2 status at screening, a blood sample will be collected to determine the status with the results available prior to randomization.
  11. Criterion modified per amendment
    - 11.1 Criterion modified per amendment
    - 11.2 Have all of the following:
      - hemoglobin  $\geq 9$  g/dL (without transfusion in the prior 7 days). Subjects may be enrolled into the study while receiving recombinant erythropoietin provided they have received recombinant erythropoietin for at least 4 weeks before the first dose of study drug.
      - albumin  $\geq 25$  g/L
      - absolute neutrophil count (ANC)  $\geq 1,500/\mu\text{L}$
      - platelet count  $\geq 100,000/\mu\text{L}$  (without transfusion in the prior 7 days)
      - either a serum creatinine  $\leq 1.5$  mg/dL or a calculated glomerular filtration rate  $\geq 60$  mL/min/1.73 m^2 (Cockcroft-Gault) ([Attachment 6](#))
      - CPK  $\leq 2.5$  x upper limit of normal (ULN)
  12. Have total bilirubin  $\leq$ ULN. If total bilirubin is  $>$ ULN, measure direct and indirect bilirubin to evaluate for Gilbert's syndrome (if direct bilirubin is within normal range, subject may be eligible).
  13. Have alkaline phosphatase (ALP)  $\leq 2.5$ xULN; if the ALP is  $>2.5$ xULN, then an ALP liver fraction or 5' nucleotidase must be  $\leq$ ULN (as reported in absolute units of measure).
  14. Have AST and ALT  $\leq 2.5$ xULN.
  15. Have LVEF by MUGA scan or 2D-ECHO within normal limits for the institution.
  16. Have side effects (except alopecia) of prior treatment resolved to at least Grade 1 according to the National Cancer Institute – Common Terminology Criteria of Adverse Events (NCI-CTCAE) Version 4.0 (except for those laboratory criteria listed in eligibility criterion #11).
  17. Have a negative pregnancy test (urinary or serum  $\beta$ -human chorionic gonadotropin [HCG]) at screening (applicable to women of child bearing potential).
-

---

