**6.1. Criteria for Continuation of Treatment**

On Day 1 of each subsequent treatment cycle (Cycle 2 and beyond), the criteria specified in Table 1 must be met in order for treatment to occur. If the criteria in Table 1 are not met on Day 1 of a new cycle, the subject must be evaluated at least weekly and the new cycle will start upon recovery to the Day 1 criteria specified in Table 1. Dosing may be delayed for a maximum of 3 weeks to allow for recovery of toxicity. If toxicity does not resolve after 3 weeks of delay, the subject must discontinue treatment. If it is determined that a subject can continue treatment, it may be necessary to reduce the dose of study drug based on maximum toxicity or critical analytes or toxicities, that occurred since the previous dose as described in Section 6.2, Dose Modification.

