**Table 1: Criteria for Continuation of Treatment**

Variable	Day 1
Platelets	≥100,000/μL
ANC	≥1,500/μL
Hemoglobin	≥9 g/dL
Bilirubin	≤ ULN
ALP	≤2.5 x ULN; unless ALP liver fraction or 5' nucleotidase is normal a
Albumin	≥25 g/L
Transaminases	≤2.5 x ULN
Creatine phosphokinase	≤2.5 x ULN
Serum creatinine	≤1.5 mg/dL
LVEF b	≥LLN
Other nonhematologic, drug-related effects	Grade 2 or lower

ALP=alkaline phosphatase; ANC=absolute neutrophil count; LVEF=left ventricular ejection fraction; LLN=institutional lower limit of normal; ULN=upper limit of normal

a If the results of the ALP liver fraction or 5' nucleotidase are not yet available because of the length of time required to obtain these results, the subject may receive the study drugs to avoid a treatment delay only if on an earlier assessment, total ALP had a similar value and the ALP liver fraction or 5' nucleotidase was ≤ULN, confirming that the ALP elevation was of osseous origin. ALP liver fraction should be reported and evaluated in absolute units of measure.

b As determined by the most recent LVEF assessment.

Treatment should be discontinued for subjects who experience liver abnormalities that include all of the following within the same cycle:

- bilirubin ≥2 x ULN,
- transaminases (ALT or AST) ≥3 x ULN, and
- ALP (liver fraction) <2 x ULN (as reported in absolute units of measure).

Subjects must discontinue DOXIL for clinical evidence of cardiac toxicity or if the LVEF is compromised (ie, any absolute decrease in LVEF ≥10% and an LVEF value below the institutional lower limit of normal [LLN]). However, dosing with trabectedin should continue if the criteria for continuation of treatment are met (Table 1) and at the same dose. For those subjects on treatment Arm A who continue with trabectedin as a monotherapy after a cumulative anthracycline dose of 300 mg/m^2 has been exceeded or due to cardiotoxicity, regular monitoring of LVEF every 2 cycles of treatment should continue, regardless of the cumulative dose of anthracycline. All subjects in Arm A should undergo LVEF assessments after Cycle 3 of study treatment, even if DOXIL has been discontinued.

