## 6.2. Dose Modification

Dose reductions will be made on the basis of the worst drug-related toxicity. However, investigators may also reduce the dose of either or both study drugs for toxicity, as clinically warranted. Dose reductions will be made on the basis of the worst drug-related toxicity that occurred since the previous dose, except for reductions due to AST or ALT increases that should only be based on Day 15 toxicity; see Section 6.2.1, Dose Reductions Due to Hematologic

Toxicity, and Section 6.2.2, Dose Reductions Due to Nonhematologic Toxicity. Table 2 and Table 3 specify the dose levels that will be used when dose reductions are required for subjects in the trabectedin+DOXIL combination therapy group or DOXIL monotherapy group, respectively. Subjects who experience toxicities that require more than 2 dose reductions of the same drug must discontinue treatment with that drug. If trabectedin is discontinued for a subject in Treatment Arm A, premedication with dexamethasone is no longer required. Dose escalations are not allowed following a dose reduction for toxicity.

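### Table 1 bars every dose from Cycle 2 when bilirubin exceeds ULN, with no exception for subjects whom inclusion criterion #12 can admit above ULN with normal direct bilirubin

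*Protocol*

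**What the plan says.** **Entry.** Criterion #12 in Protocol 4.1 requires total bilirubin no higher than ULN. If it is higher, the direct and indirect fractions are measured to look for Gilbert's syndrome, and "if direct bilirubin is within normal range, subject may be eligible".

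**Dosing from Cycle 2.** Section 6.1 states that "the criteria specified in Table 1 must be met in order for treatment to occur". If they are not met on Day 1, "the subject must be evaluated at least weekly and the new cycle will start upon recovery" to the Table 1 values. It continues: "Dosing may be delayed for a maximum of 3 weeks to allow for recovery of toxicity". Then: "If toxicity does not resolve after 3 weeks of delay, the subject must discontinue treatment".

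**Table 1.** The bilirubin row gives a limit of ULN with no footnote and no alternative test. The alkaline phosphatase (ALP) row gives its limit and then adds "unless ALP liver fraction or 5' nucleotidase is normal", with a footnote on how to proceed while that result is pending.

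**Discontinuation.** Section 10.2 lists failure to meet the Section 6.1 criteria among the reasons why treatment should be discontinued.

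**Dose reduction.** Table 5 (Section 6.2.2) lowers trabectedin by one level for any bilirubin above ULN and leaves DOXIL unchanged. Section 6.2 sets the general basis: "Dose reductions will be made on the basis of the worst drug-related toxicity that occurred since the previous dose".

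**The concern.** The entry rule and the dosing rule treat the same laboratory value differently, and Table 1 first applies at Cycle 2. A subject with total bilirubin above ULN and normal direct bilirubin can be randomized and dosed once, and then refused her next dose although nothing has changed. She has advanced relapsed cancer, so a withheld dose matters to her. Her site also has no written rule on how long the delay lasts or how it ends, and two sites could handle the same case differently.

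What is at stake is treatment delivery and consistency between sites, not the primary analysis.

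**Working it through.** The plan gives no figure to reproduce here, so the check is to set the rules side by side and follow one subject through them.

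**Which entry exceptions reach Table 1?**

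| Item | Entry (Protocol 4.1) | Table 1, Cycle 2 onward |
|---|---|---|
| Bilirubin | Total at or below ULN, or above ULN with normal direct bilirubin (#12) | At or below ULN; fraction not named; no alternative |
| ALP | At or below 2.5 x ULN, or higher with liver fraction or 5' nucleotidase at or below ULN (#13) | Same limit, same alternative |
| Renal function | Creatinine at or below 1.5 mg/dL, or calculated GFR at or above 60 mL/min/1.73 m² (#11) | Creatinine limit only |

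The ALP exception carries over and also appears as a footnote to Table 5. The bilirubin exception appears only at entry. The GFR alternative is missing from Table 1 as well.

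**Which fraction does Table 1 mean?** The row says only bilirubin. Criterion #12 compares total bilirubin with ULN and names the direct fraction when it means that, so total is the natural reading. As background, the amendment log records that INT-3 replaced direct bilirubin with bilirubin in Table 5. A direct-bilirubin reading of Table 1 would remove the conflict, but the current text does not state it.

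**One subject, total bilirubin above ULN throughout, direct bilirubin normal.**

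1. Screening: she may be eligible under #12.
2. Cycle 1: she is dosed, because Table 1 does not yet apply.
3. Cycle 2 Day 1: she fails the bilirubin row. This is Day 1 + 21 = Day 22 in Arm A and Day 1 + 28 = Day 29 in Arm B. No dose is permitted.
4. Rechecks at the minimum weekly frequency: Days 29, 36 and 43 in Arm A (22 + 21 = 43), and Days 36, 43 and 50 in Arm B (29 + 21 = 50). A full 3-week delay therefore means being above ULN at four checks in a row. One value at or below ULN lets the cycle start.
5. End of the delay: the mandatory stop in Section 6.1 is worded for toxicity that has not resolved. If an unchanged entry value is not toxicity, that sentence does not apply, but nothing permits dosing either. Section 10.2 then says that treatment should stop because Section 6.1 is not met. The text does not settle the outcome.

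**Does anything else release her?** Neither the protocol nor the SAP exempts these subjects. Section 17.1 lets the site and sponsor agree on how to handle an unavoidable departure, case by case. That is not a standing exception.

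**Table 5.** Read alone, its bilirubin row would also reduce trabectedin for this subject. Section 6.2 ties the required reductions to drug-related toxicity, so an unchanged, non-drug-related baseline value should not trigger it. That row needs a clarification, not a new rule.

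**Can an exception be operated?** Yes. Direct and indirect bilirubin are already in the chemistry panel (Sections 9.1.3.1 and 9.5).

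**The case against.** The best defense is that the stricter on-treatment limit was deliberate. Trabectedin is hepatotoxic: Section 1.2.2 reports Grade 3 or 4 ALT in 32% of subjects on the combination against 1% on DOXIL alone in the earlier Phase 3 study. Table 1 is also not a copy of the entry criteria. It is looser for other nonhematologic drug-related effects (Grade 2 or lower, against Grade 1 for residual side effects of prior treatment at entry) and stricter for creatinine. The retained ALP exception therefore does not prove that every entry exception was meant to carry over.

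This stands as a caution about intent, which the documents state neither way. It does not remove the conflict. A deliberate bar from Cycle 2 makes little sense for a subject admitted knowingly above that limit, and the same row gates Arm B, which receives no trabectedin.

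Three stronger readings are tempting and are not supported:

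- *Affected subjects must be withdrawn after 3 weeks.* That follows only if the stable value is read as toxicity, and a single qualifying recheck restarts dosing.
- *The plan penalizes a value already shown to be benign.* Criterion #12 asks for an evaluation and says the subject may be eligible. It requires neither a confirmed Gilbert's diagnosis nor a repeat showing stability, and it accepts the value for entry only.
- *The survival comparison is compromised.* The gate applies in both arms, all randomized subjects are analyzed, and survival follow-up continues after treatment stops.

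**Conclusion.** The concern holds as a minor error in the wording. Followed exactly, the rules can admit and dose a subject once and then bar her from Cycle 2 at an unchanged, accepted bilirubin. This rests on reading the Table 1 row as total bilirubin. If direct was intended, the row still has to say so.

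The number of subjects affected is not given and cannot be derived from the documents, so no frequency or hazard-ratio effect is quoted. That the effect on overall survival is negligible is a judgement from the design features listed above, not a calculation. The practical reach is essentially before Amendment 6, after which trabectedin stops, randomization ends and any continued DOXIL follows local standard of care. What remains of use is in interpreting past delays or discontinuations, and in correcting these tables if they are reused.

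**What to change.** **Table 1.** Footnote the bilirubin row to accept, as an alternative for subjects enrolled above ULN under #12, a direct bilirubin within the normal range together with no clinically meaningful rise in total bilirubin from screening. The sponsor should set the margin; the documents offer no basis for a particular number. Name the fraction in the row itself.

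**Table 5.** Note that the bilirubin row does not apply to an unchanged baseline elevation that is not drug-related. This agrees with Section 6.2.

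**Leave unchanged** the transaminase and ALP limits and the combined stopping rule in Section 6.1: "Treatment should be discontinued for subjects who experience liver abnormalities that include all of the following within the same cycle".

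**Cost.** No new assessments are needed. Bilirubin gating becomes slightly looser in a hepatotoxic regimen, limited by the direct-bilirubin condition, the comparison with screening and the retained rules. The change alters a dosing criterion, so it is not purely administrative and needs ethics committee or IRB approval before use (Sections 16.2.2 and 17.1).
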